5.3 Lottery incentive for CVD risk assessment

The goal of the second intervention is to evaluate the effectiveness of the PhilPEN program in delivering primary prevention of CVD. This will be achieved by offering randomly selected respondents a ticket for a lottery with a money prize on condition that they visit a RHU/CHC for a checkup. There will be one prize per barangay giving each respondent a one in ten chances of winning P5000 (US\$100). The prize is equivalent to approximately 14 days earnings at the regional minimum wage⁵. This *randomized encouragement design* will induce exogenous variation in patients accessing the PhilPEN program allowing its impact to be estimated.

As noted in Section 3.1, there are potential weaknesses in implementation of the PhilPEN program and the purpose of this component of the experiment is to establish the effectiveness of the program as it is currently implemented. For that reason, there is no supply-side component to the intervention. Respondents will simply be told that they can enter a lottery if they go to the RHU/CHC for a checkup. The health facilities will be told to conduct an assessment deemed appropriate for any particular patient that requests to be issued with a lottery ticket. No instructions will be given that the facilities should follow the PhilPEN protocol. We will evaluate whether they do implement the protocol for patients who qualify (by age if nothing else) for full risk screening.

The remainder of this sub-section describes the logistics of the lottery intervention.

Designating a RHU/CHC point person. The agreement will state that the MHO/CHO should designate a point person in the RHU/CHC facility who will be responsible for handing out the lottery tickets. This should be one of the medical staff (e.g. the rural health nurse, midwife or the MHO/CHO, or PhilPEN coordinator) who performs or delegates the performance of the PhilPEN profiling and screening. The identity of this point person will be included in the information provided by enumerators to the lottery recipients.

Voucher and ticket. A voucher will be given by the enumerator to those deemed eligible for the lottery intervention at the end of the interview. This voucher will be surrendered at the facility to the RHU/CHC point person in exchange for a lottery ticket. The voucher and ticket will both be pre-numbered with the same number.

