- b. *After the interview.* If the respondent is deemed eligible for the lottery intervention, the enumerator will read from a prepared script informing that the respondent is eligible to enter the lottery and that they can claim the ticket from a designated point person at the health center. The script will make it clear that the voucher only entitles them to a lottery ticket and that their name will not be entered if they do not claim the ticket by attending the RHU/CHC for a checkup. The script will also make it clear that they can only claim the ticket after a certain date (possibly two days from receipt of the voucher) and only until a specific date (one month after the interview). The script will also inform the respondent the prize money for the lottery and the chance of winning. The enumerators will be given a prepared answer to give if they are asked whether everyone can enter the lottery. The enumerator will ask the respondent to sign a form indicating that they have understood the terms of the voucher and the lottery.
- c. *Tagging the recipients*. The respondents who receive the vouchers will be tagged by the survey firm. The questionnaire will include fields that indicate whether the respondent is eligible, whether the respondent received the voucher, the date of the receipt of the voucher, and the voucher number.

Instructions to the RHU/CHC point person. To verify the identity of the person claiming the lottery ticket, the point person will be instructed to ask for the name, address, birthday and age as of last birthday, and mobile number of the respondent or any family member. These details will be recorded on a form to be submitted to UPecon. The point persons will not be explicitly instructed to follow the PhilPEN protocol. Rather, they will be told to assess the patients claiming the lottery ticket as they would any other person attending the RHU/CHC for an assessment. Given the sample only contains individuals aged 40+, recording of the person's age should alert the RHU/CHC that, consistent with the PhilPEN protocol, screening should be conducted.

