The primary sampling unit (PSU) and the level at which treatment will be randomly allocated is the barangay. The is the lowest administrative unit in the Philippines. There are 849 barangays in Nueva Ecija. Barangays will be randomly drawn for inclusion in the study and randomly allocated to one of the two treatment groups or the control group with probabilities set to achieve the required sizes of the groups.

Within a barangay, interval sampling will be used: starting from a random location, a procedure will be followed to randomly select households moving out from that point. Selected households will be screened to establish whether each includes anyone aged from 40 to 70 inclusive. If so, one such person will be randomly selected as the main survey respondent and the potential subject of the intervention in the treatment group barangays. Further screening will be undertaken to establish whether the selected person is eligible for the study, mainly on the basis of CVD history (see next section). In addition to the main respondent, we will ask the head of household, spouse or other adult to answer questions about the household in general.

9. Inclusion and exclusion criteria

We restrict attention to individuals aged 40 and above because this is one of the criteria for proceeding from risk assessment to risk screening under the PhilPEN protocol. Hence, we know that all respondents

induced to go for a checkup should be given a full screen with tests for blood glucose, urine protein and, if available, blood lipids. By restricting attention to the 40+ age group, we focus on the population in which CVD risks begin to rise steeply and preventive care is most needed. In addition, Globorisk predicts 10-year CVD risk only for individuals aged 40-74. We exclude those older than 70 because comorbidities are likely to rise steeply beyond that age, and because older individuals are likely to be more cognitively challenged in responding to the risk perceptions and risk attitudes questions.

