We will exclude from the study individuals who report that they have been diagnosed as having heart disease or diabetes, or who report that they have had a heart attack or a stroke. This is consistent with the study's focus on primary prevention of CVD. Those with heart disease, or who have had a heart attack or stroke, can benefit from secondary prevention. But examination of demand for and the effectiveness of such care would require another sampling strategy to identify a sufficiently large pool of potential beneficiaries. We exclude those with a diagnosis of diabetes because the office based version of Globorisk we will use substantially underestimates the 10-year CVD risk for those with diabetes.

Those currently (past 2 weeks) taking medication for hypertension will also be excluded because they are already receiving primary prevention of CVD. Respondents who report that they have been diagnosed with hypertension will be included provided they are not currently taking antihypertensives. Hence, those who are not adhering to this medication will be included in all components of the study. Those taking medication for diabetes will be excluded, although this should be a redundant exclusion criterion given those with a diagnosis of diabetes are excluded.

After completing a household roster to identify if there is anyone aged 40-70 and selecting one such person, there will be a short screening module to identify and eliminate anyone who meets the exclusion criteria defined in the previous two paragraphs. Also excluded will be those who have some medical problem that prevents measurement of blood pressure or BMI.

10. Power analysis

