10.1 Parameter values

To the extent that it is possible given the estimates available, we have strived to base the choice of parameter values on evidence. However, it must be acknowledged that, as is often the case with power calculations, the evidence is often lacking or meagre, and we often must resort to guesstimates. In doing so, we have endeavoured to err on the side of conservatism and have conducted sensitivity analyses.

Power

Power is set to 80% and statistical significance to 5%.

Minimum detectable effect size

We calculate the sample size necessary to detect a small effect size (δ) defined as 0.2 standard deviation (SD) units (Cohen 1992). Consider our main outcome i) – the 10-year risk of a heart attack or stroke predicted by the office-based Globorisk algorithim. Given an estimated mean 10-year CVD risk of 11.35% in the control group, which we obtain from Globorisk for individuals aged 40-69 with mean values of all risk factors, if the standard deviation is one fifth of the mean, then an effect size of 0.2 SD corresponds to a 4% reduction in the mean. The assumption that the standard deviation is one fifth of the mean is based on estimates of the distribution of 10-year CVD risk scores (Gale et al 2014; Gray et al 2014). However, we caution that these estimates are not obtained using the Globorisk algorithm and most are for samples of high-income country populations.⁷

We deliberately choose a small effect size in order to ensure that our samples will be sufficient to detect only marginal impacts of the interventions on the risk factors that determine the CVD risk prediction. The logic is threefold. First, risk factors such as smoking and weight are notoriously hard to influence. Second, our information intervention is of unknown effectiveness and we recognize a possibility that a non-negligible fraction of respondents are unable to absorb the information provided on their CVD risks. Third, while the procedures defined by the PhilPEN protocol are proven to be effective, our aim is to establish effectiveness as the program is implemented, which may fall well short of the stipulated testing, medication and counselling.

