For mean systolic blood pressure (outcome iii), mean BMI (v) and mean waist circumference (viii), we obtain the estimated control group means from measures taken in the 2013 National Nutrition Survey (NNS) for individuals aged 40-69 (FNRI-DOST, 2015). The standard deviation is assumed to be one seventh of the mean for systolic blood pressure, one fifth of the mean for BMI and one ninth of the mean for waist circumference based on Ezzati et al (2004). In each case, we set the minimal detectable effect size to 0.2 SD units of the mean.

Control group proportions for elevated blood pressure (outcome iv), overweight/obese (vi), smoking (vii), central adiposity (ix), undiagnosed hypertension (x) and hypertension medication (xi) are also taken from the 2013 NNS for individuals aged 40-69. For these binary outcomes, we set the minimal detectable effect size to the small value defined by Cohen (1992) as 0.2 of his h-index.

Intra cluster correlation

⁷ Using the Framingham algorithm for 10-year CVD risk (D'Agostino et al 2008), Gale et al (2014) report a mean of 14.3% and a standard deviation of 2.59 for an English sample of 60+, non-frail persons with no history of CVD. A small study of 40+ employees without previous CVD in a region of Wales reports means (standard deviations) of non-laboratory based Framingham 10-year CVD risk of 10.7% (2.4) for males and 4.8% (1.2) for females (Gray et al 2014).

To the best of our knowledge, there are no estimates available of the intra cluster correlation for (predicted) 10-year CVD risk with clusters defined by communities resembling the size of Filipino barangays. Some idea of the correlation is given by ICCs for CVD risk factors, which determine predicted risk. Table 3 provides estimates of such ICCs for clusters defined at the level of primary care practice obtained from three North American studies.

While homogeneity of CVD risk factors within Filipino barangays need not necessarily closely resemble the homogeneity observed within primary care practices in North America, these estimates at least give an idea of the ICC that might be expected. We set the ICC at 0.1, which is almost twice the highest estimate for any risk factor in Table 3. This is even more conservative than might appear at first sight since one would expect there to be even less within community homogeneity in CVD risk predicted on the basis of all risk factors than there is in each individual risk factor individually.

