10.2 Results

Required sample sizes under the main scenario for parameter values described in the previous sub-section are given in Table 6. Estimates under alternative scenarios are given in Appendix B Tables B1-B4. The requisite sample size differs little across the outcomes but is slightly larger for the binary outcomes. We will set the sample size to that required to have sufficient power to test for the specified minimal effect size on the binary outcomes under the main scenario.

Table 6: Sample size calculations – Main scenario (1)

	Mean CVD risk	Mean systolic BP in mm Hg	Mean BMI	Mean waist circumference in cm	Binary outcomes
Required sample sizes					
Info treatment per round (unadjusted)	287	293	287	293	299
Lottery treatment per round (unadjusted)	1,306	1,333	1,306	1,333	1,361
Control per round (unadjusted)	1,306	1,333	1,306	1,333	1,361
Total baseline sample (adjusted)	4,816	4,916	4,816	4,916	5,019
Total follow-up sample	2,899	2,959	2,899	2,959	3,021
Number of clusters	290	296	290	296	303
Avg. cluster size at baseline	16.61	16.61	16.61	16.61	16.56

In implementing the sampling design, we will sample 303 barangays out of 849 distributed across the 32 municipalities and cities in Nueva Ecija province. We will meet with the mayors of all 32 municipalities to introduce the study, get their consent and endorsement of our field activities within their jurisdiction. This will be done during the field mobilization phase (see Table 2).

Since treatment will be randomized at the barangay level, there is no issue of contamination across households within a barangay. But since one RHU/CHC typically serves more than one barangay (there are 63 RHU/CHCs in the province), contamination through the same facility serving both treatment and control barangays needs to be considered. This is not an issue for the information intervention and control groups since the former does not require that the RHU/CHC do anything. The facility will be unaware of patients that belong to these two groups. There could be an issue if the role of the RHU/CHC in implementation of the lottery causes it to operate differently for all patients. One possibility is that it

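### Barangay randomisation stops arms mixing within a barangay, but it does not protect screening, consent and baseline beliefs collected while vouchers and risk figures are already being handed out there

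*Combined protocol and SAP*

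**What the plan says.** Section 10.2 states "Since treatment will be randomized at the barangay level, there is no issue of contamination across households within a barangay" and then considers only spillover through health facilities that serve barangays in different arms.

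The order of fieldwork has to be put together from other sections:

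- **Allocation comes first.** Barangays are drawn and assigned before local officials are visited (5.1).
- **Households are taken in sequence.** Within a barangay, "starting from a random location, a procedure will be followed to randomly select households moving out from that point" (Section 8).
- **Screening is at the household and by self-report.** It follows the roster and the random pick of one person aged 40 to 70. "Those currently (past 2 weeks) taking medication for hypertension will also be excluded", as are people reporting diagnosed heart disease or diabetes, or a past heart attack or stroke (Section 9).
- **Consent is taken before each baseline interview** (Section 12). In lottery barangays the form carries an extra line about passing the respondent's details to the health facility (5.3, interview procedure, item a). A separate lottery consent form is also planned (Section 12).
- **Delivery happens during the same survey.** Risk figures are given inside the beliefs module (5.2, Section 6). For the lottery, "A voucher will be given by the enumerator to those deemed eligible for the lottery intervention at the end of the interview" (5.3).
- **Questions are expected.** "The enumerators will be given a prepared answer to give if they are asked whether everyone can enter the lottery" (5.3, item b).

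No section completes screening, consent or baseline beliefs across a barangay before the first delivery there. The possible two-day wait in 5.3 delays claiming the ticket, not learning of the lottery.

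**The concern.** In a cluster trial that recruits after allocation, randomisation balances the clusters but not the people who enter from them. Here the step that decides entry and the step that delivers treatment run side by side in the same barangay.

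In lottery barangays, word of a 5,000 PHP prize, or the arm-specific consent line itself, could change who agrees to take part and how people answer the screening questions. Nothing comparable happens in control barangays. Outcome xi (antihypertensive use in the last two weeks) is most directly exposed: someone who hides current use to qualify, and reports it at follow-up, is counted as new uptake.

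In information barangays, later respondents may have heard neighbours' figures before giving their section B answers (perceived base rate) or section D answers (perceived personal risk). Section B enters H2b to H2d and H2f. Section D supplies the prior in equation 3.1 (H3a, H3d) and the treated-versus-control contrast in D.

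**Working it through.** **1. The plan's own figures.** Inputs from Section 10.1 and Table 4: 5% significance (two-sided reproduces), 80% power, effect 0.2 SD, ICC 0.1, 10 per cluster at follow-up, correlation 0.6, compliance 60%.

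- Per arm before compliance: 2 × ((1.960 + 0.842)/0.2)² = 392.4; × 1.9 (design effect 1 + 9 × 0.1) × 0.64 (1 − 0.6²) = 477.2.
- Per arm after compliance: 477.2/0.36 = 1,325.6. Table 6 gives 1,306 to 1,361.
- Baseline total, binary outcomes: 3,021/[(1 − 0.10 − 0.15 − 0.05) × 0.86] = 3,021/0.602 = 5,018. Table 6 gives 5,019.

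The sample size reproduces. It uses one 15% refusal rate and one 14% ineligibility rate for all arms, so it makes no allowance for differential entry.

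**2. How many people are in question.** Table 6 samples 16.56 per barangay; 16.56 × 0.86 × 0.85 = 12.1 are eligible and consent. At 10 per cluster there are about 1,361/10 = 136 lottery and 299/10 = 30 information barangays. How many of the 12 are reached after a neighbour has been treated depends on enumerators and days per barangay, which the plan does not give.

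**3. Outcome xi, on assumed concealment.** Take Table 5's 10% on medication as the share of current users, and let a share *c* of them conceal it in lottery barangays only. The values of *c* are assumptions.

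- Concealers as a share of the enrolled arm: 0.10*c*/(0.86 + 0.10*c*), which is 1.15% at *c* = 0.1 and 3.37% at *c* = 0.3. These are upper bounds for each *c*, because some users are also excluded for other reasons.
- Bias, net of the 10% who would be on medication at follow-up anyway: × 0.90 gives 1.03 and 3.03 points.
- Offered-versus-control target: 0.6 × (16 − 10) = 3.6 points.
- SE = √[(0.10 × 0.90 + 0.136 × 0.864) × 1.9 × *k*/1,361], which is 1.36 points at *k* = 0.64 and 1.70 at *k* = 1. The second is the more natural, since nobody enrolled should report current use at baseline and the baseline value then explains nothing.
- Two-sided 5% rejection with no true effect: 9–12% at *c* = 0.1 and 43–61% at *c* = 0.3.

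**4. Differential consent, also assumed.** If refusal in lottery barangays fell from 15% to 10% or 5%, extra consenters would be 0.05/0.76 = 6.6% or 0.10/0.81 = 12.3% of that arm. If they differ by 0.2 to 0.5 SD in outcome, the unadjusted bias is 0.013 to 0.062 SD, or 11–51% of the 0.12 SD contrast (0.6 × 0.2). If baseline adjustment leaves 40% of it (assumed), that is about 4–21%.

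**5. Beliefs.** The lottery arm is left out of the belief tests (footnote 3, Section 3.2). Information respondents are 299/(299 + 1,361) = 18% of pooled section B tests, which limits any distortion there. Equation 3.1 uses the information arm alone, so it has no such dilution.

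**6. Would a check by arm detect it?** About 1,361/0.602 = 2,261 people are sampled per lottery or control arm. For ineligibility of 14% against 11%, power is 86% if clustering is ignored. With 16.56 per barangay it falls to 63% at ICC 0.05 and 48% at ICC 0.1 (ICCs for screening answers are assumed). The check would often find a sizeable shift, but a null result would not rule one out.

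**The case against.** The strongest reply is that Section 10.2 is discussing contamination between arms, and on that it is correct. This stands: there is no contradiction to remove, only a scope to state. A reader might infer that the sentence is false and should be deleted; the documents do not support that.

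A reader might also infer that about 11 of every 12 respondents are recruited after a treated neighbour. That needs one enumerator per barangay and neighbours who talk between interviews. The plan gives neither enumerator numbers nor the distance between sampled households. Household and respondent selection is meant to be random, so the exposed steps are mainly availability, screening answers, consent and baseline answers.

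Nor do the documents support reading the 43–61% rejection rate as a forecast for outcome xi. Concealment requires people to know that medication disqualifies them, and the voucher script in 5.3 covers prize, chance, dates and claim rule but not the exclusions. They would also have to report use honestly at follow-up.

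The principal outcome, predicted CVD risk, rests largely on measured blood pressure and BMI and is adjusted for its baseline value, so it is less exposed. In H2f, the direct comparison of section D with section B uses controls only.

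What remains is that nothing in the plan prevents arm-dependent entry or would reveal it. The manuals, penalties and spot checks in Section 14 address whether procedures are followed; they do not conceal the arm.

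**Conclusion.** The gap is real and limited. The sequence follows from the documents, and Section 10.2 does not address it. It leaves entry to the lottery arm and beliefs in the information arm open to influence after allocation. Whether bias arises, and how large it is, cannot be known from the plan.

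On the assumed rates above, bias in outcome xi could be small (about 1.0 point) or most of the 3.6-point target (about 3.0 points). Bias in a continuous outcome could be about 4–21% of the sized contrast after adjustment. For beliefs, the updating weight in equation 3.1 and the section D contrast are the most exposed; direction and size cannot be derived.

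This warrants a change in wording, forms and reporting. It does not invalidate the design. Without the checks, a positive result on xi would be hard to separate from selective entry.

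**What to change.** - Limit the Section 10.2 sentence to spread between arms, and state that recruitment follows allocation.
- Use the same screening and consent wording in all three arms. Move the line on sharing details with the facility to the additional lottery consent form already planned in Section 12.
- Have the tablet show arm-specific content only once the respondent has been screened and has consented. This shields the respondent's entry decision, though not from neighbours or from an enumerator who knows the arm; hence the next items.
- Record interview order within each barangay, using the interview timing that Section 14 already requires.
- Report refusal and ineligibility, including reported antihypertensive use, by arm and order. Control barangays show what order alone does, so the informative quantity is the arm-by-order difference, with clustering allowed for.
- Repeat the section B and D tests and outcome xi by interview order as sensitivity analyses. First interviews alone give only about 30 information respondents, so use order as a trend or in bands.

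Optional where fieldwork allows: finish screening and consent across a barangay before any delivery, or hand out vouchers in one round after its last baseline interview. In 303 barangays the first may mean a second pass and some losses between passes, and it would still leave section B asked after neighbours had been informed unless those questions moved too.

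The cost is minor form and tablet changes and a little more analysis. Sample size and number of barangays are unchanged.
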